4 STUDY DESCRIPTION

The first part of this Phase 2b study was conducted as a multicenter, randomized, double-blind, placebo-controlled study. Each subject's total study duration was no more than 10 weeks and total active dosing days were 25 days. 72 subjects were randomized in a 3:1 ratio to active treatment or placebo, respectively. 54 subjects received active treatment and 18 received placebo. Randomization was stratified on baseline weekly CSBM rate. Subjects with baseline CSBM rates of 1.0-3.0/week were randomized to begin with 75 mg of ENT-01 (3 tablets) or 3 placebo tablets: subjects with baseline CSBM rates of 0-0.9/week were randomized to begin with 150 mg of ENT-01 (6 tablets) or 6 placebo tablets. The dose was then escalated every 3 days in increments of 25 mg (or 1 placebo tablet) until either an effective dose, a maximum tolerated dose or 250 mg was reached, whichever came first. The dose was then "fixed" at that dose for the remainder of the 25-day treatment period.

In this amendment of the protocol, the study will be conducted as a multicenter, randomized double-blind, placebo-controlled study. Each subject's total study duration will be no more than 10 weeks and total active dosing days will be 25 days. Up to 80 subjects will be randomized across up to 25 U.S. sites to ensure approximately 60 subjects will complete all visits, assuming a 25% early termination rate. Randomization will be 1:1 to active treatment or placebo.

Randomization will be stratified based on baseline weekly CSBM rate. Subjects with baseline CSBM rates of 1.0-3.0/week will be randomized to begin with 75 mg of ENT-01 (3 tablets) or 3 placebo tablets: subjects with baseline CSBM rates of 0-0.9/week will be randomized to begin with 150 mg of ENT-01 (6 tablets) or 6 placebo tablets. The dose will then be escalated every 3 days in increments of 25 mg (or 1 placebo tablet) until either an effective dose, a maximum tolerated dose or 250 mg is reached, whichever comes first. The dose will then be “fixed” at that dose for the remainder of the 25-day treatment period. The dosing logic is illustrated in the diagram below.

- The subject will be randomized to either placebo or ENT-01, with the starting number of tablets based on the baseline CSBM rate.
- The dose will be escalated every 3 days by 1 tablet (25mg ENT-01 or placebo)
- If the subject passes at least 1 CSBM/day on each of 3 consecutive days the dose is “fixed.” Otherwise, the dose is escalated.

Throughout the study, subjects will keep daily electronic stool diaries. The stool diaries will record information including stool frequency, consistency, ease of evacuation, completeness, and the use of rescue medication. Stool related information will be entered immediately upon completing the bowel movement. This information will be collected electronically through web-based questionnaires that the subjects and/or their caregivers complete. Site staff will monitor these entries regularly to ensure that subjects are not at risk of becoming impacted and are using rescue medication as directed. Site staff will contact subjects if the web-based questionnaires are not being completed on a daily basis or if there are any concerns about a subject's safety.

Rescue medication (suppositories and enemas) will be provided to subjects and will be initiated in the evening of the third day if a subject has had no bowel movement for three consecutive days.

Symptoms of Parkinson's Disease will be assessed using the Movement Disorder Society's Unified Parkinson's Disease Rating Scale (MDS-UPDRS) during “ON” states, approximately one hour after levodopa intake (if applicable).

If the “ON” time is not 60 minutes after L-Dopa, assessment has to occur at “ON” time or whenever the subject is “ON”.

Subjects who prematurely discontinue study drug for any reason will be asked to have an Early Termination (ET) visit within 3 days following the last study drug dose. If a subject discontinues study drug during a scheduled visit, then the Early Termination visit should be conducted at that time. These subjects will also be asked to complete the Wash-Out period and return for the End of Study (EoS) Visit.

Study (EoS) Visit. The stool sample (if applicable) should be collected during the ET visit if the subject does not wish to return for the EoS Visit.

Figure 1: Study Design

Visit Schedule Overview					
Visit 1	Visit 2	Visit 3	Visit 4	Visit 5	Visit 6
Screening	Randomization and Drug Dispensation	Follow up	End of Treatment – Beginning of Single Blind Placebo Withdrawal	End of Single blind Placebo – Beginning of Wash Out	End of Study
Day -21	Day 1 +/- 8days	Day 10 +/- 3 day	Day 26 - 2 days	Day 39 +/- 8 days	Day 69 +/- 8 days

Commented [A2]: Should this be +8days or +/- 8days

4.1 Visit 1: Screening Visit (Study days -21 to -1)

The purpose of the baseline or “screening” period is to establish constipation severity off laxatives. At the end of the screening period the subject’s eligibility will be assessed by an

Evaluation Committee.

During Visit 1, the following assessments and procedures will be performed:

- Informed consent
- Inclusion/Exclusion Criteria
- Demographics/Medical History
- Complete Physical Exam
- Height
- Weight
- Orthostatic Vital Signs – 3 sets: Vital signs will include supine blood pressure and heart rate, sitting or standing blood pressure and heart rate, respiratory rate, and body temperature. Sitting or standing measurements will be taken approximately 5 minutes after the subject has been sitting or standing. The sets should be taken throughout the Visit and not sequentially.
- 12-lead ECG
- Labs and urinalysis: as defined in [APPENDIX 1](#).
- Pregnancy Testing – For women of child-bearing potential, this is done on-site with the urine pregnancy kit (UPT) provided. If the on-site UPT is positive, then a serum pregnancy test will be done. For post-menopausal women less than 60 years or age, a serum FSH will be done at the screening visit only.
- Instructions to Discontinue Laxatives and other Constipation medications. All prescription laxatives (Linzess, Amitiza), over the counter laxatives (Miralax, Ex-lax, Bisacodyl/Dulcolax), suppositories (Bisacodyl/Dulcolax), enemas (Fleets), and dietary supplements to increase bowel movements (chia seeds, bran, fiber supplements) will be discontinued.
- Dispense Rescue Medication: Subjects will be provided with suppositories and enemas. Anytime during the study if a subject does not have any bowel movement for three consecutive days, rescue medication should be used to evacuate their bowel as directed by the

site. In the rare event that the above does not produce a bowel movement, the subject will be instructed to notify the site and ask for direction.

- Stool and laxative Diary Instructions: Subjects will be taught how to use the I-Pad for stool and laxative diaries. They will be instructed to take the I-Pad to the toilet and fill it in immediately after a bowel movement. They will be taught the definition of a CSBM. If the subject “feels like he/she is completely emptied out” and that “they have no more stool left to pass”, and the stool is not just a few pebbles, then that will be a CSBM (a complete BM). If the subject leaves the house for a few hours, they will be told to take the I-Pad with them in case they have a BM elsewhere. Each BM will be entered immediately. If no entries have been made for the day, the subject will be sent 3 reminders starting at 7pm. Laxative use will also be entered immediately into the laxative diary. Multiple uses will be entered multiple times.
- AE Review
- Prior and Concomitant Medication
- Rome IV questionnaire
- MDS-UPDRS – The MDS-UPDRS should be administered while the subject is in an ON state, approximately one hour after taking levodopa (if applicable). If the “on” time is earlier or later than 60 minutes after L-Dopa, UPDRS will be performed at that time.
- Subjects will be invited to participate in two sub-studies, consisting of obtaining levodopa PK draws pre-dose, and 20, 40 and 60 minutes post-dose at Visits 2 and 3, 4, 5 and 6 and (2) stool sample collection on Visits 2 and 4. This first twenty subjects to affirm consent will participate in the L-Dopa sub-study and the first 20 subjects to affirm consent will participate in the stool microbiome study.
- Questionnaires:
 - C-SSRS
 - SAPS-PD and hallucination interview (only those subjects who have a SAPS-PD score > 0 at the Screening Visit and Randomization Visit).
 - BDI-II
 - MMSE

- Dispense Stool Collection Kit – Subjects participating in the sub-study will be given a stool collection kit so they can bring a stool sample at Visit 2

For subjects who score > 0 on the SAPS-PD at Visit 1 and Visit 2, the SAPS-PD and hallucination interview are repeated at Visit 2.

4.2 Visit 2: Randomization (Study Day 1 + 8 days)

The purpose of this period is to establish the prokinetic dose for subjects randomized to treatment (or placebo). The prokinetic dose is the dose that results in a CSBM on all three dosing days at any given dose. Subjects will also be required to have a CSBM on at least 1 of 2 subsequent days at the “fixed” dose. In other words, *the dose will only be “fixed” for the remainder of the treatment period if the subject has CSBMs on at least 4 of 5 consecutive days at a given dose.*

In this amended study, subjects will be randomized in a 1:1 ratio to receive either ENT-01 or placebo depending on baseline weekly CSBM rate:

- Subjects with baseline CSBMs of 0-0.9 will be randomized to begin treatment with 150 mg of ENT-01 or 6 tablets of placebo.
- Subjects with baseline CSBMs of 1.0-3.0 will be randomized to begin with 75 mg of ENT-01 or 3 tablets of placebo.

Subjects will self-administer the study medication at home, beginning the day after Visit 2. The dose will be taken upon awakening on an empty stomach along with 8 oz. of water. The subject will be instructed to remain in the upright position for the next 60 minutes. This can be in the sitting or standing position, and the subject should be encouraged to walk around, go to the kitchen and make a cup of tea or coffee (with or without milk or sugar), to watch the news or read a paper in the upright position. The subject will also be instructed to not eat for at least 60 minutes thereafter.

After the first dose, the subject will be advised to stay home for 4-6 hours in case an emergency evacuation occurs. The subject can determine what to do after subsequent doses. Subjects are not allowed to miss a dose, however, in the event this does happen, subjects must wait a minimum of 5 hours post ingestion of a meal and at least 1 hour prior to the next meal to take the missed dose.

Any given dose is repeated for 3 consecutive days. If the subject has not produced a CSBM

within 24 hours of a dose on all three days at the initial dose, then they will increase their daily dose by 1 tablet (i.e., 25 mg for active treatment), repeating that dose for three consecutive days. This 3-day incremental dosing will continue until the subject:

- Reaches the prokinetic dose. The prokinetic dose is determined when a subject has entered CSBMs on at least 4 of 5 consecutive days at a given dose. The subject then remains on that dose until Visit 4;
- Reaches the maximum dose of 10 tablets (i.e., 250 mg for active treatment); or,
- Reaches the dose limiting tolerability(DLT).

If the subject has 4 or more episodes of diarrhea with a consistency of 6-7 (see [APPENDIX 6](#)) within 24 hours of a dose on 2 consecutive days at a given dose, the dose will be reduced by 25 mg and fixed at that dose assuming diarrhea subsides.

Should a prokinetic response not occur at 250 mg (or 10 tablets), subjects will continue to take 10 tablets daily for the remainder of the 25-day treatment period.

During this visit, the following assessments and procedures will be performed:

- Review of Inclusion/Exclusion Criteria
- Confirmation of eligibility: To be randomized to receive double-blind study medication in this study, subjects must meet the following criteria:
 - Have at least 11 ‘Available Data Days’ (days with e-Diary compliance sufficient for determining whether a CSBM occurred) (Subjects with fewer than 11 diary days will continue to fill in their diaries until 11 days’ worth of information is available and randomization will be delayed). Have had fewer than 3 complete spontaneous bowel movements per week based upon the average CSBM rate reported during the 2-week Screening Period. This rate will be calculated centrally with a computer-based system and requested by the site the day before randomization.
 - Be deemed eligible for randomization by the enrollment committee
 - Weight
 - Orthostatic Vital Signs
 - 12-lead ECG

- Pregnancy Testing – For women of child-bearing potential only.
- Randomization: Sites will utilize a centralized, computer-based system (IWRS) to obtain the randomization bottle (s) assigned to each subject.
- In-clinic Levodopa Dosing – Subjects will take their morning dose of levodopa in the clinic.
- Subjects will be given study medication and will take their first dose the following day at home, on an empty stomach. The day after Visit 2 will be the first day of treatment.
- Levodopa PK Draws – The first daily dose of L-Dopa will be administered in clinic. Blood samples will be obtained pre-L-Dopa dose and at 20, 40-and 60-minutes post-dose. (Applicable to the levodopa PK sub-study only.)
- Dispense Rescue Medication, as needed. Subjects continue appropriate use of rescue medication, ensuring adequate bowel movements every 3 days.
- AE Review
- Prior and Concomitant Meds
- C-SSRS
- SAPS-PD (if SAPS-PD score is greater than 0 on Visit 1 and 2, subject will have SAPS-PD and hallucination questionnaire administered at each subsequent visit).
- PAC-SYM
- PAC-QOL
- Collect Stool Sample (if participating in stool sub-study)
- Dispense IP/placebo and instruct subjects to take their second dose of study drug the following morning. Subjects will be advised to stay at home for 4-6 hours in case they need to evacuate urgently.

4.3 **Visit 3: Study Day 11 (+/- 3 days)**

The purpose of this visit is to evaluate the incidence of adverse events and to review the subject's dosing experience by reviewing ePRO entries with the subject.

During this visit, the following assessments and procedures will be performed:

- Brief Physical Exam
- Weight
- Orthostatic Vital Signs
- 12-lead ECG
- Labs and urinalysis as defined in [APPENDIX 1](#).
- Pregnancy Testing - For women of child-bearing potential only.
- For subjects participating in the L-Dopa sub-study, subjects will be instructed to come to clinic as early as possible and on an empty stomach. They will first take their study medication (ENT-01 or placebo) in clinic. Thirty minutes after the ENT-01/placebo dose, subjects will take their morning dose of levodopa.
- Levodopa PK Draws - Blood samples will be obtained before the L-Dopa dose and at 20, 40 and 60 minutes after the dose.
- IP/Placebo Drug Accountability and Dispensation
- Dispense Rescue Medication, as needed. Subjects continue appropriate use of rescue medication, ensuring adequate bowel movements every 3 days.
- Stool Diary Review
- AE Review
- Prior and Concomitant Meds
- MDS-UPDRS - The MDS-UPDRS should be administered while the subject is in an ON state, approximately one hour after taking levodopa (if applicable), or whenever the “ON” state occurs.
- Questionnaires:
 - C-SSRS
 - BDI-II
 - MMSE

- PAC-SYM
- PAC-QOL
- SAPS-PD and hallucination questionnaire (if applicable)
- Dispense Stool Collection Kit - Subjects participating in this sub-study will be given a stool collection kit so they can bring a stool sample at Visit 4.

4.4 Visit 4: End of treatment period/ Beginning of Placebo Period (Study Day 26)(- 2 days)

The purpose of the treatment period is to establish the impact of ENT-01 on CSBM rates. The purpose of the placebo period is to determine the duration of the treatment effect once study medication is discontinued. At this visit, all subjects will be given placebo and will continue taking the same number of tablets as they were taking at the maximum “fixed” dose period. The subject will not be made aware that the study medication provided is a placebo.

During this visit, the following assessments and procedures will be performed:

- Brief Physical Exam
- Weight
- Orthostatic Vital Signs – 3 sets: See screening description
- 12-lead ECG
- Labs and urinalysis as defined in [APPENDIX 1](#).
- Pregnancy Testing - For women of child-bearing potential only.
- IP/Placebo Collection and Accountability
- Single-blind Placebo Dispensation
- For subjects participating in the L-Dopa sub-study, subjects will be instructed to come to clinic as early as possible and on an empty stomach. They will first take their study medication (ENT-01 or placebo) in clinic. Thirty minutes after the ENT-01/placebo dose, subjects will take their morning dose of levodopa.
- Levodopa PK Draws - Blood samples will be obtained before the -L-Dopa dose and at 20,

40 and 60 minutes after the dose

- IP/Placebo Collection and Accountability
- Dispense Rescue Medication, as needed. Subjects continue appropriate use of rescue medication, ensuring adequate bowel movements every 3 days.
- Stool Diary Review
- AE Review
- Prior and Concomitant Meds
- MDS-UPDRS - The MDS-UPDRS should be administered while the subject is in an ON state, approximately one hour after taking levodopa (if applicable), or whenever “ON” occurs.
- Questionnaires:
 - C-SSRS
 - BDI-II
 - MMSE
 - PAC-SYM
 - PAC-QOL
 - SAPS-PD and hallucination questionnaire (if applicable)
- Collect Stool Sample (if applicable)

4.5 Visit 5: End of placebo period/ beginning of Wash-Out (Study Day 39) (+/- 8 days)

The purpose of the Wash-out period is to determine the duration of treatment effect. Subjects will be taken off placebo (study medication). They will continue to keep daily stool diaries for the duration of this period. During the first 3 weeks, subjects will continue to use rescue medication as needed. The following day, i.e., day 22 of the Wash-Out Period, subjects will be instructed to restart all their original medications, including oral laxatives.

During this visit, the following assessments and procedures will be performed:

- Brief Physical Exam
- Weight
- Orthostatic Vital Signs
- 12-lead ECG
- Labs and urinalysis as defined in [APPENDIX 1](#).
- For subjects participating in the L-Dopa sub-study, subjects will be instructed to come to clinic as early as possible and on an empty stomach. They will first take their study medication (placebo) in clinic. Thirty minutes after the placebo dose, subjects will take their morning dose of levodopa.
- Levodopa PK Draws - Blood samples will be obtained before the -L-Dopa dose and at 20, 40 and 60 minutes after the dose.
- Pregnancy Testing - For women of child-bearing potential only.
- Dispense Rescue Medication, as needed. Subjects continue appropriate use of rescue medication, ensuring adequate bowel movements every 3 days.
- IP/Placebo Collection and Accountability
- Stool Diary Review
- AE Review
- Prior and Concomitant Meds
- MDS-UPDRS - The MDS-UPDRS should be administered while the subject is in an ON state, approximately one hour after taking levodopa (if applicable), or whenever “ON” occurs.
- Questionnaires:
 - C-SSRS
 - BDI-II

- MMSE
- PAC-SYM
- PAC-QOL
- SAPS-PD and hallucination questionnaire (if applicable)

4.6 Visit 6: End of Study Visit (Study Day 69) (+/- 8 days)

This is the final visit of the trial. During this visit, the following assessments and procedures will be performed:

- Brief Physical Exam
- Weight
- Orthostatic Vital Signs
- 12-lead ECG
- Labs and urinalysis as defined in [APPENDIX 1](#)
- Pregnancy Testing - For women of child-bearing potential only.
- In-clinic Study Medication and Levodopa Dosing - Subjects will be instructed to come to clinic as early as possible. They will take their first morning dose of levodopa in the clinic.
- Levodopa PK Draws - Blood samples will be obtained before the -L-Dopa dose and at 20, 40 and 60 minutes after the dose.
- IP/Placebo Drug Accountability
- Stool Diary Review
- AE Review
- Prior and Con Meds
- MDS-UPDRS - The MDS-UPDRS should be administered while the subject is in an ON state, approximately one hour after taking levodopa (if applicable), or whenever “ON” occurs.

- Questionnaires:
 - C-SSRS
 - BDI-II
 - MMSE
 - PAC-SYM
 - PAC-QOL
 - SAPS-PD and hallucination questionnaire (if applicable)

4.7 Early Termination Visit (if appropriate)

If a subject terminates the study prematurely for any reason, the following procedures will be performed:

- Complete physical examination, including weight
- Orthostatic vital signs
- 12-lead ECG
- Laboratory studies and urinalysis
- Blood draw for L-Dopa PK sub-study only. Blood samples will be obtained pre-dose and at 20, 40, and 60 minutes post-dose. (Applicable to the L-Dopa PK sub-study only. Subjects will take their dose of ENT-01/matching placebo 30 minutes prior to taking L-Dopa.
- Pregnancy testing, for women of child-bearing potential only.
- IP/Placebo collection and accountability
- Electronic stool diary review
- Review of AEs
- Prior and concomitant medications
- MDS-UPDRS should be administered while the subject is in an ON state, approximately one hour after taking L-Dopa (if applicable)
- Subjects will complete the following questionnaires:
- BDI-II

- MMSE
- PAC-SYM
- PAC-QoL
- If subjects discontinue from the study prior to Visit 4, collect Stool Sample (as applicable)

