Informed Consent	X						
Inclusion/Exclusion Criteria ^a	X	X					
Demographics/Medical History	X						
Complete Physical Exam	X						X
Brief Physical Exam			X	X	X	X	
Height	X						
Weight	X	X	X	X	X	X	X
Orthostatic Vital Signs ^b	X	X	X	X	X	X	X
12-lead ECG	X	X	X	X	X	X	X
Labs and Urinalysis	X		X	X	X	X	X
Pregnancy Testing ^c	X	X	X	X	X	X	X
In-clinic IP/Placebo Dosing ^d			X	X	X		
In-clinic Levodopa Dosing		X	X	X	X	X	X
Levodopa PK Draws ^e		X ^e	X ^e	X ^e	X ^e	X ^e	X ^e
IP/Placebo Dispense		X	X	X			
IP/Placebo Collection and Accountability			X	X	X	X	X

Commented [A1]: Confirm whether +/- 8 days or only +8 days

CONFIDENTIAL

19April21 7.0

	Visit 1 Screening	Visit 2 Randomization	Visit 3 Follow-Up	Visit 4 End of Treatment	Visit 5 End of Placebo	Visit 6 End of Study	Early Termination
	Day -21	Day 1 (+/-8 days)	Day 11 (+/- 3 day)	Day 26 (- 2 days)	Day 39 (+/- 8 days)	Day 69 (+/- 8 days)	
Instructions to Discontinue Laxatives and other BM Medications	X						
Dispense Rescue Medications ^f	X	X	X	X	X		
Stool Diary Instruction/Review ^g	X	X	X	X	X	X	X
AE Review	X	X	X	X	X	X	X
Prior and Con Meds	X	X	X	X	X	X	X
Rome IV questionnaire	X						
MDS-UPDRS ^h	X		X	X	X	X	X
C-SSRS	X	X	X	X	X	X	X
BDI-II	X		X	X	X	X	X
MMSE	X		X	X	X	X	X
SAPS-PD, Hallucination/Delusion Questionnaire ⁱ	X	X	X	X	X	X	X
PAC-QOL and PAC-SYM		X	X	X	X	X	X
Dispense Stool Collection Kits	X		X				
Collect Stool Sample ^j		X		X			X

CONFIDENTIAL**19April21_7.0**

a. Confirmation of eligibility: To be randomized to receive double-blind study medication in this study, subjects must meet the following criteria:

- Have had at least 11 "Available Data Days" (days with electronic diary compliance sufficient for determining whether a BM occurred)
- Have had <3 CSBMs/week based upon the average CSBM rate during the first 2 screening weeks (baseline period).
- Be approved for randomization by the enrollment committee

b. Three sets will be taken. Time points to be defined. Orthostatic vital signs will be taken in the supine position and will include BP and HR, sitting or standing BP and HR, RR, and body temperature. . Sitting or standing measurements will be taken within approximately 5 minutes of sitting or standing.

c. For women of child-bearing potential, on-site with urine pregnancy test kit. If the on-site UPT is positive, a serum pregnancy test will be done. For post-menopausal women <60 years or of age, a serum FSH will be done at the screening visit only.

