c. For women of child-bearing potential, on-site with urine pregnancy test kit. If the on-site UPT is positive, a serum pregnancy test will be done. For post- menopausal women <60 years or of age, a serum FSH will be done at the screening visit only.

d. Sites will use a centralized computer-based system to obtain the randomization bottle(s) assigned to each subject.

- Subjects with baseline CSBMs from 0 to 0.9 will be randomized to begin treatment with ENT-01 150 mg or 6 tablets of placebo.
- Subjects with baseline CSBMs from 1.0 to 3.0 will be randomized to begin treatment with ENT-01 75 mg or 3 tablets of placebo.
- Subjects will self-administer study medication at home. The dose will be taken upon awakening, on an empty stomach with 8 oz. of water.
- Subjects will be advised to stay at home for 4 to 6 hours after taking the first dose of medication in case there is a need to evacuate urgently. After the first dose, subjects will know if and when to leave the house.

e. A subset of 20 subjects from this study population will participate in an L-Dopa PK Study, as follows:

- Visits 2 and 6: Blood draws for L-dopa levels (PK) will be drawn at Time zero.
- The first daily dose of L-Dopa will be administered on site after the first blood draw. There will be another blood draw at 20, 40, and 60 minutes post- L-Dopa dose
- Visits 3, 4, and 5: Immediately upon arrival at the study site, the subject will take study medication (ENT-01 or placebo) on an empty stomach. Blood will be drawn at Time zero. 30 to 60 minutes after taking ENT-01 or placebo, the subject will take their first daily dose of L-Dopa. Blood will be drawn again 20, 40, and 60 minutes post-L-Dopa dose. The subject may have food 60 minutes after taking ENT-01.

f. Rescue medications will be dispensed as needed and instructions given concerning laxatives and other medications to treat constipation.

g. Subjects will be educated concerning use of the electronic diary to report stools immediately after a bowel movement

h. The first 3 parts of the MDS-UPDRS should be administered while the subject is in an ON state, approximately one hour after taking L-Dopa (if applicable). In some cases, patients will reach the “on” state earlier or later than at 60 minutes. In those cases, MDS-UPDRS should be performed when the patient is “on”.

i. Those subjects who have a SAPS-PD score >0 on Visits 1 and 2 will have the SAPS-PD and hallucination/delusion questionnaire at all subsequent visits.

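### Protocol Section 4.7 has L-Dopa sub-study subjects take study drug at the Early Termination visit, with no exception for those already off drug (minor)

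*Protocol*

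**What the plan says.** Protocol Section 4.7 lists the procedures for any subject who terminates early, whatever the reason. For the L-Dopa PK sub-study it asks for blood samples before the dose and at 20, 40 and 60 minutes after it, and adds: "Subjects will take their dose of ENT-01/matching placebo 30 minutes prior to taking L-Dopa". Nothing limits this to subjects still on study drug.

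Section 4 of the Protocol describes two kinds of ET visit:
- In the usual case, anyone stopping treatment early "will be asked to have an Early Termination (ET) visit within 3 days following the last study drug dose", which means that dosing is over by the time of the visit.
- In the other case, the ET visit is merged with a planned one: "If a subject discontinues study drug during a scheduled visit, then the Early Termination visit should be conducted at that time".

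The Schedule of Events appears in Protocol Table 1, Protocol Appendix 2 and SAP Table 1. In all three, the row "In-clinic IP/Placebo Dosing" is marked at Visits 3, 4 and 5 and is blank at ET. The rows for in-clinic levodopa dosing and levodopa PK draws are marked at ET.

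Footnote e to these tables sets the sub-study regimen. For the visits with study drug it reads: "Visits 3, 4, and 5: Immediately upon arrival at the study site, the subject will take study medication (ENT-01 or placebo"). For Visits 2 and 6 it gives L-Dopa alone. It has no line for ET, although the ET cell of the PK row in Protocol Table 1 carries the footnote e mark.

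**The concern.** A site running an ET visit a day or two after the last dose has two instructions that cannot both be followed. Section 4.7 says to give study drug before L-Dopa. The schedule has levodopa dosing and PK draws at that visit but no study-drug dose.

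Two things are at stake. The first is subject safety. Protocol Section 5.6 provides for withdrawal because of an adverse event, and Sections 3.1 and 8.15 list individual stopping criteria such as a marked fall in blood pressure or liver tests above three times the upper limit of normal. A subject stopped for one of these could be given one more blinded dose solely to obtain an exploratory PK profile. The second is the data. ET profiles would be with or without a fresh study dose depending on which text the site followed, in a sub-study meant to show whether ENT-01 changes levodopa absorption.

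**Working it through.** The plan states no figure on this point, so there is nothing to reproduce. The check is a comparison of texts, followed by a rough count.

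**Texts by type of ET visit**

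1. *ET visit held after the last dose, during the 25-day treatment period.* By the Section 4 definition, dosing has ended. The schedule has no study-drug dose at ET. Section 4.7 requires one. This is a conflict, and the dose could be ENT-01.
2. *ET visit held after the last dose, between Visits 4 and 5.* The same conflict of text applies. All subjects have been on placebo since Visit 4 (Section 4.4), so a further dose would be inert.
3. *ET visit during wash-out.* Section 4.5 says of subjects at this stage: "Subjects will be taken off placebo (study medication"). They have no current dose, so the sentence cannot be carried out and re-doses nobody.
4. *ET visit merged with Visit 3, 4 or 5.* Footnote e has the subject take study drug on arrival, so the day's dose may already have been taken before drug is stopped. If so, there is no conflict. If it is still due, no text says whether to give it.

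Real exposure to ENT-01 is therefore confined to ENT-01 subjects who stop during the treatment period.

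**Rough count**

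Inputs:
- Sub-study size N: 20 (Protocol Section 4.1; footnote e in Protocol and SAP) or 10 (SAP Section 2.6.3). The SAP gives both.
- Early termination rate r: 25% (Protocol Sections 4 and 5.1) or 10% (drop-out rate in the power calculation, Protocol Section 9.2.5). Applying either to the sub-study is an assumption.
- ENT-01 share: 0.5, from the 1:1 ratio now in force.
- Fraction of terminations falling in the treatment period: 25/69 = 0.362, assuming they are spread evenly to Day 69.

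Expected ENT-01 subjects = N × r × 0.5 × 25/69:
- 20 × 0.25 × 0.5 × 0.362 = 0.91
- 20 × 0.10 × 0.5 × 0.362 = 0.36
- 10 × 0.25 × 0.5 × 0.362 = 0.45
- 10 × 0.10 × 0.5 × 0.362 = 0.18

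The even spread matters. If every termination fell within the treatment period, the largest case would be 20 × 0.25 × 0.5 = 2.5. Drop-out driven by adverse events would move the count in that direction and raise the ENT-01 share. In the other direction, all these counts include merged visits and stops that have nothing to do with safety.

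**The case against.** The best defence is that other text already limits the effect. Section 5.6 sends early-discontinuation visits to the Schedule of Events, and Section 8.0 says procedures follow that schedule, which has no ET dose. The possessive in Section 4.7 (the subject's own dose) can be read as presupposing a current dose, which a discontinued subject lacks. Sections 8.13 and 11.7 let the investigator depart from the protocol in an emergency or to remove an immediate hazard. This lowers the practical risk but does not cancel the sentence. Sections 8.13 and 11.7 do not cover a routine withdrawal, and Section 11.8 asks for instructions to be followed exactly and grants no waivers.

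A reader might also infer more than the documents support:

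- *That footnote e contradicts Section 4.7.* It does not. It says nothing about ET, which is a gap. The conflict rests on Section 4 and the dosing row of the schedule.
- *That collecting drug at the ET visit shows none should be given there.* Section 4.7 does list "IP/Placebo collection and accountability", but the schedule marks both dosing and collection at Visits 3, 4 and 5, so the two routinely occur together.
- *That the sentence should simply be deleted.* Deletion would leave the ET draws with no stated regimen and would not deal with a dose still due at a merged visit.
- *That the count should use the 3:1 ratio.* This gives 20 × 0.25 × 0.75 × 0.362 = 1.36, but the Protocol describes the 3:1 cohort as already conducted, and a change now cannot affect it.

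The Visit 6 bullet in Section 4.6, which opens "In-clinic Study Medication and Levodopa Dosing - Subjects will be instructed to come to clinic as early as possible", names study medication and then gives only levodopa. That is a separate wording slip and adds nothing to this point.

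**Conclusion.** The inconsistency is real and minor. For an ET visit held after study drug was stopped, Section 4.7 conflicts with the timing in Section 4 and with all three copies of the schedule, and footnote e supplies no regimen to resolve it. Taken literally, it re-doses a subject withdrawn from drug.

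Roughly one or fewer ENT-01 subjects would be expected to be exposed at the current 1:1 ratio (0.2 to 0.9). These are expected counts under assumed drop-out rates and even timing, and they are not bounds. The documents do not say how many subjects stop for safety reasons, how ET visits divide between separate and merged, or whether the sub-study places were already filled before version 7. The sub-study is exploratory, so the primary efficacy analysis and the power are unaffected. The case for acting is that the error concerns dosing after withdrawal and a wording change removes it.

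**What to change.** Make the sentence in Section 4.7 conditional:

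- At an ET visit held after study drug was discontinued, give no ENT-01 or placebo. Give L-Dopa alone, with draws before it and at 20, 40 and 60 minutes after it, as at Visits 2 and 6.
- If ET is merged with Visit 3, 4 or 5 and that day's dose was already taken, record its time. If it was not yet taken and drug is being discontinued, do not give it.

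Add a matching ET line to footnote e in Protocol Table 1, Protocol Appendix 2 and SAP Table 1.

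The cost is a short wording change in both documents. Section 11.7 requires regulatory and IRB approval of any amendment, across up to 25 sites, so it is best carried in the next one. ET profiles after discontinuation will be collected without a fresh study dose, which is what the schedule already implies.
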